### **11.1 Case Report Form**

An eCRF is a printed, optical, or electronic document designed to record the protocol required information to be reported to the sponsor on each study subject.

For each subject who has given informed consent the eCRF must be completed and signed by the investigator (or authorised designee) to certify the data are complete and correct. Where the eCRF is not the source document, the investigator must maintain accurate documentation (source data) to support information entered in the eCRF.

Management of clinical data will be performed in accordance with Third Party Biostatistics and Data Management Vendor applicable standards and data cleaning procedures with oversight by GSK CH to ensure integrity of the data, for example, to correct/remove errors and inconsistencies in the data.

To protect the privacy of subjects, no Personal Information (PI) (including the subject's name or initials or full birth date) is to be recorded in the eCRF or as part of the query text.

All eCRF pages should be completed during a subject assessment when the eCRF has been designated as the source. Data that is sourced elsewhere should be entered into the eCRF in an agreed upon timeframe between the Investigator and Sponsor.

GSK CH will obtain and retain all eCRFs and associated study data as applicable at the completion of the study.

### **11.2 Data Handling**

Documentation of all data management activities should allow step-by-step retrospective assessment of data quality and study performance.

Any changes or corrections to data will be performed in the Electronic Data Capture (EDC) System, and it will include rationale for changes. The EDC system has an audit trail, which will provide a complete record of the changes and corrections endorsed by the investigator.

Property of GSK Consumer Healthcare - Confidential

May not be used, divulged, published or otherwise disclosed without the consent of  
GSKCH

CCI

Clinical Protocol Template v7.0

Page 76 of 100

Adverse events will be coded using Medical Dictionary for Regulatory Activities (MedDRA) and any concomitant medications terms (if applicable) using WHODrug.

### 11.2.1 Data Queries

Programmed edit checks will be generated automatically, as the data are being entered into the system. Reports and listings on the eCRF data will also be run, in addition to the queries already programmed and generated by the system, to raise manual queries as needed for site clarification or correction. A query should be issued to update the verbatim towards a codable description.

The study monitor will perform ongoing review of the eCRFs in accordance with the monitoring plan, to confirm that data entered into the eCRF by authorised site personnel are accurate, complete and verifiable from source documents; that the safety and rights of participants are being protected; and that the study is being conducted in accordance with the currently approved protocol and any other study agreements, ICH GCP and all applicable regulatory requirements.

Any queries will be generated in the EDC System to the investigator or designee, enabling the errors to be addressed in parallel with Data Management review. The study monitor can also run reports and listings on the eCRFs, to raise manual queries as needed for site clarification or correction.

### 11.3 Processing Subject Reported Outcomes

Paper-based subject reported outcome (SRO) data will be collected from the product usage diary and DHEQ and entered into the eCRF.

All SRO source data should be reviewed by the study staff and the study monitor to ensure accurate transcription of data and that any potential AEs or concomitant medications reported on these documents are discussed with the subject and transcribed accurately to the eCRF. SROs that are classed as source data will be retained by the investigator and true/certified copies may be sent to a designated vendor or GSK CH as required.

To protect the privacy of subjects, no Personal Information (PI) (including the subject's name or initials or full birth date) is to be recorded on any SRO that will be forwarded to GSK CH or Third-Party Vendor.

Property of GSK Consumer Healthcare - Confidential

May not be used, divulged, published or otherwise disclosed without the consent of  
 GSKCH

CCI

Clinical Protocol Template v7.0

Page 77 of 100

#### **11.4 External Data**

Subject data generated externally to the eCRF from laboratory instruments, computers or other sources and then transcribed into a file and format agreed upon by GSK CH is termed external data. No external data will be generated during the conduct of this study.

### **12 STATISTICAL CONSIDERATIONS AND DATA ANALYSES**

#### **12.1 Sample Size Determination**

No formal sample size has been produced for this PoP clinical study to investigate changes in sensitivity measures (Schiff sensitivity score, tactile threshold and number of sensitive teeth) over time with twice-daily use of a novel combination toothpaste. Based on previous, similar GSK CH studies evaluating the sensitivity protection provided by daily-use toothpastes, approximately 30 evaluable subjects per product group is considered sufficient to provide reliable estimates of performance for the purposes of this study and to aid in the design of future clinical studies. Approximately 120 subjects will be randomised to study product.

From a previous, similar GSK CH study (GSKCH Clinical Study 209723, 2020), change in Schiff sensitivity score at Week 8 had an SD of 0.7 units and the degree of variability (SD) in the test and control groups remained roughly consistent with each other over time. A similar trend was observed for the tactile threshold and number of sensitive teeth endpoints.

A sample size of 30 evaluable subjects per product group is expected to provide 95% CIs with a width of  $\pm 0.261$  units for the Schiff sensitivity score. This level of precision is considered sufficient for the purposes of this study. Approximately 120 subjects will be randomised to study treatment.

Property of GSK Consumer Healthcare - Confidential

May not be used, divulged, published or otherwise disclosed without the consent of  
GSKCH

CCI

Clinical Protocol Template v7.0

Page 78 of 100

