**Type and Planned Number of Subjects:**

The study will be conducted in male and female subjects in good general health, aged 18-65 years inclusive, with pre-existing self-reported tooth sensitivity and at least two sensitive teeth (confirmed clinically) that meet all study criteria at both the Screening (Visit 1) and Baseline (Visit 2) visits.

Sufficient subjects will be screened to ensure approximately 120 subjects are randomised to study product (approximately 30 subjects per product arm); approximately 30 evaluable subjects per product group is considered sufficient to provide reliable estimates of performance for the purposes of this study and to aid in the design of future clinical studies.

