## 4.2 Scientific Rationale for Study Design

The study will investigate the ability of an experimental combination toothpaste containing 3% weight/weight (w/w) PVM/MA + 5% w/w KNO3 (Test Product), a 3% w/w PVM/MA only toothpaste (Comparator 1), a 5% w/w KNO3 only toothpaste (Comparator 2) and a regular fluoride toothpaste with no known anti-sensitivity properties (negative control) to protect sensitive teeth from DH. Trends in sensitivity measures over time (from Baseline to 8 weeks) will be investigated for each product group as the primary objective. Inter-product comparisons will be investigated as secondary objectives; comparisons between the Test and Comparator toothpastes will be of particular interest to explore if the combination toothpaste provides enhanced sensitivity protection.

The randomised, controlled, examiner-blind, parallel design selected for this study follows the recommended approach for investigating the performance of sensitivity products.

Use of two independent stimulus-based (tactile and evaporative (air)) measures of tooth sensitivity is in line with published recommendations for the design and conduct of sensitivity clinical studies. The selection of two 'test teeth' to evaluate changes in DH is also common practice in sensitivity studies (Schiff et al., 1994). Eligible subjects will be stratified after the Baseline assessments according to the maximum Schiff sensitivity score of their two selected 'test teeth' to ensure product groups are balanced for sensitivity severity.

Study subjects will be aged between 18 and 65 years; DH most frequently occurs between the ages of 20 and 40 years and is known to decrease with age above 40 years (Bartold, 2006, West et al., 2014, Dababneh et al., 1999).

According to ICH guidelines, for a study to be classed as truly double blind, not only does the examiner (and any appropriate member of staff who may be involved in the dispensing of products, analysis of data etc.) need to be blinded as to the product the subject receives, but the products under test must be identical in every way (colour, flavour, appearance, packaging). Given it is almost impossible to ensure identical appearance, taste and packaging for the toothpastes evaluated in oral care studies, the level of product blinding for this study is described as 'examiner blind'. Study toothpastes will be supplied in over-wrapped tubes. The blind will be maintained by staff involved in dispensing, brushing

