## 5 STUDY POPULATION

### 5.1 Type and Planned Number of Subjects

The study will be conducted in male and female subjects in good general health, with pre-existing self-reported tooth sensitivity and at least two sensitive teeth (clinically confirmed DH) that meet all study criteria at both the Screening (Visit 1) and Baseline (Visit 2) visits. Sufficient subjects will be screened and entered into the acclimatisation phase to ensure approximately 120 subjects are randomised to study product (approximately 30 subjects per product arm). Subjects will be recruited primarily from the study site database.

This study can fulfill its objectives only if appropriate subjects are enrolled. The following eligibility criteria are designed to select subjects for whom participation in the study is considered appropriate. All relevant medical and non-medical conditions should be taken into consideration when deciding whether or not a subject is suitable.

Eligibility to participate should be reviewed and documented by an appropriate member of the study site team before each subject is included in the study.

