#### **Change from Baseline in tactile threshold (g) at Day 3, Weeks 2, 4 and 8**

Tactile threshold (g) and change from Baseline will be derived as for the Schiff sensitivity score. The change in tactile threshold (g) will be analysed at each time point using an ANCOVA model with product and Baseline Schiff stratification included as factors and Baseline tactile threshold included as a covariate.

For both Change from Baseline in Schiff sensitivity score and Change from Baseline in tactile threshold, using the above models, adjusted mean change from Baseline, along with 95% CIs will be reported by product group. P-values testing for non-zero change from Baseline will also be presented for each product group. Mean difference between product groups, 95% CIs and p-values will also be provided. Significance testing will be conducted at the two-sided 5% significance level; no adjustment for multiple comparisons will be made.

Property of GSK Consumer Healthcare - Confidential

May not be used, divulged, published or otherwise disclosed without the consent of  
 GSKCH

CCI

Clinical Protocol Template v7.0

Page 80 of 100

In each case, the assumptions of the ANCOVA model will be investigated. An appropriate data transformation or non-parametric method may be performed in case of strong model violations.

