### **12.3.7 Handling of Dropouts and Missing Data**

Subjects who withdraw from the study early will be included in the statistical analysis up to the point of withdrawal. Subjects who withdraw will not be replaced. No data will be imputed in the case of dropouts or missing data.

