1.4 Sample Size Calculation

No formal sample size has been produced for this PoP clinical study to investigate changes in sensitivity measures (Schiff sensitivity score, tactile threshold, and number of sensitive teeth) over time with twice-daily use of a novel combination toothpaste. Based on previous, similar GSK CH studies evaluating the sensitivity protection provided by daily-use toothpastes, approximately 30 evaluable subjects per product group is considered sufficient to provide reliable estimates of performance for the purposes of this study and to aid in the design of future clinical studies. Approximately 120 subjects will be randomized to study product.

From a previous, similar GSK CH study (GSK CH Clinical Study 209723, 2020), change in Schiff sensitivity score at Week 8 had standard deviation (SD) of 0.7 units and the degree of variability in the test and control groups remained roughly consistent with each other over time. A similar trend was observed for the tactile threshold and number of sensitive teeth endpoints.

A sample size of 30 evaluable subjects per product group is expected to provide 95% Confidence Intervals (CIs) with a width of ± 0.261 units for the Schiff sensitivity score. This level of precision is considered sufficient for the purposes of this study. Approximately 120 subjects will be randomized to study treatment.

2 Planned Analyses

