4.4.2.1.2 Statistical Hypothesis, Model and Method of Analysis

Study product differences will be tested under the null hypothesis:

- H_0 : there is no treatment difference
- H_1 : there is a treatment difference

The following study product comparisons will be analyzed:

- Test product versus negative control
- Test product versus comparator 1
- Test product versus comparator 2

Change in Schiff sensitivity score at Day 3, Weeks 2, 4, and 8 will be analyzed using an Analysis of Covariance (ANCOVA) model which will include study product as a factor and baseline Schiff sensitivity score as a covariate. Since the baseline Schiff sensitivity score will be included as a covariate, the baseline Schiff stratification value will not be included in the model.

Using the above model, adjusted mean change from baseline, along with 95% CIs will be reported by study product group. P-values testing for non-zero change from baseline will be presented for both study product groups. Mean difference between study product groups, 95% CIs and p-values will be provided for Schiff sensitivity score in Table 14.2.2.4.1. Significance

3% PVM/MA + 5% KNO₃ Toothpaste
218220

testing will be conducted at the two-sided 5% significance level; no adjustment for multiple comparisons will be made.

The assumption of normality and homogeneity of variance in the ANCOVA model will be investigated, and if violated, an appropriate data transformation or non-parametric method, for example, the van Elteren test, adjusting for baseline Schiff stratification, will be performed.

4.4.2.2 Secondary Efficacy Variable 2

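### Does the ±0.261 precision figure mislead about between-product differences, and do 30 randomised per arm leave too little room for dropout?

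*Protocol*

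**What the plan says.** Protocol 12.1 and SAP 1.4 say that no formal sample size was produced. They give an SD of 0.7 units for the Week 8 change in Schiff score, taken from an earlier study, and say that variability was roughly alike in test and control groups. Protocol 12.1 continues: "A sample size of 30 evaluable subjects per product group is expected to provide 95% CIs with a width of" ±0.261 units. SAP 1.4 repeats the figure and adds "This level of precision is considered sufficient for the purposes of this study". The synopsis carries the same idea: "approximately 30 evaluable subjects per product group is considered sufficient to provide reliable estimates of performance for the purposes of this study".

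Protocol 5.1 plans that "approximately 120 subjects are randomised to study product (approximately 30 subjects per product arm". On missing data, Protocol 12.3.7 states: "Subjects who withdraw will not be replaced. No data will be imputed in the case of dropouts or missing data". SAP 4.4.4 agrees.

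Between-product comparisons are secondary, but Protocol 4.2 says that "comparisons between the Test and Comparator toothpastes will be of particular interest to explore if the combination toothpaste provides enhanced sensitivity protection". Protocol 12.3.2 promises intervals for them ("Mean difference between product groups, 95% CIs and p-values will also be provided"), and SAP 4.4.2.1.2 does so for the Schiff score ("Mean difference between study product groups, 95% CIs and p-values will be provided for Schiff sensitivity score in Table 14.2.2.4.1").

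**The concern.** Three things catch the eye.

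- **No label.** The SD quoted is for a change, the ±0.261 is said to be for the score, and it is called a width although a ± figure is a half-width. The text never says whether it belongs to a mean, a mean change or a difference.
- **No figure for differences.** Precision is called sufficient for the study's purposes, and those include Test-versus-other contrasts with 95% intervals at four visits. A reader who applied ±0.261 to those contrasts would think them tighter than they are. Because the study is meant to inform later designs, that misreading could carry forward.
- **No slack for dropout.** Randomised per arm equals evaluable per arm, withdrawals are not replaced and nothing is imputed. Any loss by Week 8 takes the number below the one behind ±0.261.

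**Working it through.** **Inputs.** SD of change 0.7 and 30 evaluable per product (Protocol 12.1); about 120 randomised to four arms (Protocol 5.1); two-sided 95% intervals and an ANCOVA with product and baseline score (Protocol 12.3.2). The documents give neither a dropout rate nor a correlation between baseline and change, so any value used for these below is an assumption.

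**Reproducing the stated figure.** One product's mean change, using that arm's own SD:

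t(0.975, 29) × 0.7/√30 = 2.045 × 0.1278 = 0.2614, the plan's ±0.261.

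Other readings do not fit. The normal approximation gives 0.2505, and a difference between two products gives 0.354 to 0.362. If 0.261 were a full width, about 111 subjects per arm would be needed. So the figure can be identified: it is a one-product half-width.

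**The interval the planned model gives for one product.** The Schiff ANCOVA pools variance over four arms and fits five parameters, so it has 4n − 5 degrees of freedom. With no gain from the covariate, the half-width is t(0.975, 4n − 5) × 0.7/√n:

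| Evaluable per arm | Own-arm SD | Pooled ANCOVA |
|---|---|---|
| 30 | 0.261 | 0.253 |
| 29 | 0.266 | 0.258 |
| 28 | 0.271 | 0.262 |
| 27 | 0.277 | 0.267 |
| 25 | 0.289 | 0.278 |

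**Between-product difference at n = 30.** The standard error is 0.7 × √(2/30) = 0.1807.

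- Two arms, 58 df: 2.002 × 0.1807 = 0.362.
- Pooled, 115 df: 1.981 × 0.1807 = 0.358.

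The ratios to the stated figure are 0.3618/0.2614 = 1.38 and 0.3580/0.2614 = 1.37. If baseline correlates 0.3 to 0.5 with change (assumed), the residual SD is 0.7 × √(1 − r²) and the pooled half-width falls to 0.342 or 0.310.

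**Dropout.** 120/4 = 30 randomised per arm, equal to the 30 evaluable. Under an assumed 10% loss, 27 remain: ±0.277 (own-arm) or ±0.267 (pooled) for one product, and ±0.382 or ±0.378 for a difference. The own-arm figure moves by 0.277 − 0.261 = 0.016 units on a scale that runs from 0 to 3.

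**What the precision has to serve.** The primary objective is to describe each product's profile over time. Protocol 12.3.1 and SAP 4.4.1.2 present it descriptively with no formal test. Protocol section 3 sets no formal success criterion and only expects the combination to be directionally better. The one-product half-width is therefore the relevant figure for the objective that the sample size supports.

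**The case for a change.** The best case for a change is that precision is the only quantitative justification offered for the sample size, so it should be stated for each kind of interval the study will report. The comparisons of particular interest are the differences. Their half-width is 37% to 38% larger than the one given, and ±0.261 for a difference would take about 56 evaluable per arm. Baseline adjustment narrows the gap but, at the assumed correlations, does not close it. Week 8 losses are also foreseeable: under Protocol 5.5, a subject who breaks a lifestyle restriction before that visit and cannot be reappointed is withdrawn without assessment. A few words would settle all of this.

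The arithmetic stands, and so does the observation that the label and the second figure are absent. The step to a needed change does not:

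- The ± sign and the per-group n already indicate a one-arm half-width, and the preceding paragraph names the change at Week 8. Nothing in either sample-size section mentions a difference, a target effect or power.
- Both 30 and 120 are approximate, and evaluable is not tied to Week 8. Under Protocol 12.2, mITT membership needs one use of product and one post-baseline assessment, available from Day 3, so losses mainly affect the later visits.
- Rewording the protocol would need an amendment, with ethics committee approval where required (Protocol 13.3.1), and would still leave an approximate figure. The own-arm ±0.261 is not exactly the interval that the planned ANCOVA reports (±0.253), and ±0.36 is before an adjustment whose gain is unknown.
- Adding a 10% loss scenario would put into the protocol a rate that the documents do not support.

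**Conclusion.** No change to the plan is called for. The ±0.261 is arithmetically right and is the appropriate quantity for the per-product primary objective. What is missing is a label and a companion figure of about ±0.36 for differences, both of which follow directly from the SD and n already given. Every comparison will be reported with its own observed 95% interval, so the true precision of the Test-versus-Comparator differences will be visible whatever the sample-size section says.

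The lack of a stated dropout rate has a small effect. With pooled variance the stated precision is roughly kept down to 28 evaluable per arm (±0.262), and an assumed 10% loss gives ±0.267 pooled or ±0.277 on the own-arm basis. These figures assume that the SD of 0.7 from the earlier study carries over to all four arms and that the baseline covariate brings no gain; any gain would narrow the planned intervals. Someone designing a later study should take the difference figure, or better the observed intervals, and not ±0.261 when planning a between-product contrast.

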## 12.2 Populations for Analysis

The Safety population will include all randomised subjects who complete at least one use of study product. This population will be based on the product the subject received.

The modified Intent-To-Treat (mITT) population will include all randomised subjects who complete at least one use of study product and have at least one post baseline clinical performance assessment. This population will be based on the study product to which the subject was randomised. Any subject who receives a randomisation number will be considered to have been randomised.

The Per-Protocol (PP) population will include all randomised subjects who do not have any protocol deviations that could confound the interpretation of analyses conducted on the mITT.

## 12.3 Statistical Analyses

Additional details of the proposed statistical analysis will be documented in the statistical reporting and analysis plan (RAP), which will be written following finalisation of the protocol and prior to study unblinding/analysis (as appropriate).

Where a hypothesis test between products is conducted, product differences in the study variables will be tested under the null hypothesis, H0: there is no product difference, versus the alternate hypothesis (H1) that there is a product difference.

